A per protocol analysis of the primary endpoint will include endpoints that occur in patients who complete the study fully compliant with the protocol and without any major violation or deviation (defined in the SAP).

For the secondary efficacy outcomes, analyses will be performed using the primary efficacy data set.

The apixaban-to-comparator Hazard Ratio adjusted for the competing risk of death unrelated to VTE will be computed with associated two-sided 95% Confidence Interval by resorting to the Fine & Gray regression model (Fine and Gray, 1999) using treatment group and center as dummy covariates.

Apixaban will be considered non-inferior to the comparator dalteparin if the upper two-sided 95% confidence limit of hazard ratio is < 2.00. Superiority of apixaban vs. dalteparin will be tested as a secondary analysis of the primary endpoint, only after non-inferiority has been demonstrated for the experimental treatment group (apixaban) relative to the standard treatment group (dalteparin). According to CPMP/EWP/482/99 document entitled: "Points to consider on switching between superiority and non-inferiority", switching the apixaban vs. dalteparin contrast from the non-inferiority objective to the superiority objective is feasible because the trial is properly designed in accordance to the strict requirements of a non-inferiority trial.

Caravaggio Study Protocol FINAL Version 3.0, May 22nd 2018

	For the purpose of safety analyses, subjects will be categorized to the group to which they were assigned at randomization unless incorrect study treatment was received throughout the study, in which case the subject will be categorized according to the treatment received. All safety analyses will be conducted on the safety population. The term "treatment period" refers to the period between the first administration of study drug and 48 hours after the last administration of study drug. This period will be the basis for the summaries of safety.
Study Sites and Location:	Approximately 140 study sites in 11 countries are planned to enroll patients in this study

TABLE OF CONTENTS

SYNOPSIS	2
1. LIST OF ABBREVIATIONS	12

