6.4. Observations and measurements

The investigator or a delegate will complete an electronic Case Report Form (eCRF) to document the study data.

During the screening visit the investigator or delegate will obtain:

- written informed consent;
- relevant medical history;
- information on symptoms of VTE, site and confirmatory tests;
- data on type, site and staging of cancer
- date of cancer diagnosis
- data on type and timing of cancer treatment (chemotherapy, radiotherapy, surgery)
- physical exams and measure of vital signs (e.g. body weight, blood pressure, heart rate)
- pregnancy test (WOCBP only)
- the following local laboratory results:

Serum chemistry

- Total bilirubin (direct and indirect)
- Alanine transaminase (ALT)
- Aspartate transaminase (AST)
- Alkaline phosphatase (ALP)
- Serum creatinine
- CrCL

Hematology and platelet count

- Hematocrit
- White blood cell (WBC) count
- Hemoglobin
- Platelet count
- INR
- partial prothrombin time;
- concomitant medication use (within 30 days prior to screening visit);
- screening on inclusion/exclusion criteria

Investigators should provide documentation of the index VTE event (qualifying imaging) and cancer (histology reports) during the period that extends from screening period up to two weeks after randomization.

Procedures to be performed at enrollment include:

• determine if subject continues to meet inclusion/exclusion criteria;

- randomize the subject to study medication through the Interactive Web-based Randomization System (IWRS) embedded in the eCRF
- dispense study treatment.

At 4-week and 3-month follow-up visits:

The investigator or delegate will:

- assess study outcomes (i.e. suspected recurrent VTE, bleeding), including subjects
 who have discontinued study treatment. For subjects who have discontinued study
 treatment, telephone query of health status (alive, occurrence of efficacy and safety
 endpoints and AEs/SAEs) is allowed. Subjects who have new symptoms should
 undergo further assessment as clinically appropriate, preferably at the study site
 whenever feasible.
- check the following local laboratory results:

Serum chemistry

- Total bilirubin (direct and indirect)
- Alanine transaminase (ALT)
- Aspartate transaminase (AST)
- Alkaline phosphatase (ALP)
- Serum creatinine
- CrCL

Hematology and platelet count

- Hematocrit
- White blood cell (WBC) count
- Hemoglobin
- Platelet count;
- collect study medication dispensed at previous visit;

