11. FEASIBILITY

Overall, about 140 study centers in Europe and USA, will participate in the study. Each study center is expected to recruit not less than 10 patients in the 18-month recruitment period. The overall study duration (first patient in/last patient out) is estimated to be 25 months.

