**10.9.2 Laboratory evaluation**

Clinical laboratory data will be summarized for each treatment group at each measurement time point and for each patient's final post-baseline measurement in the following ways:

- (1) with descriptive statistics (mean, standard deviation, median, and range) for each measurement time point;
- (2) with descriptive statistics for the change from baseline in the measurements at each post-baseline time point;
- (3) with shift tables summarizing the frequencies of patients below, within, and above the normal ranges at each time point as compared with baseline.

All clinical laboratory values collected during the study will be listed, with values outside the normal ranges flagged for clinical evaluation.

Presentations will use SI Units.

To convert from the conventional unit to the SI unit, multiply by the conversion factor:

Parameter	Conventional Unit	Conversion Factor	SI Unit
Hematocrit	%	0.01	Proportion of 1.0
Hemoglobin	g/dL	10	g/L
RBC count	$\times 10^6/\mu\text{L}$	0.1	$\times 10^{12}/\text{L}$
WBC count	$\times 10^3/\mu\text{L}$	1	$\times 10^9/\text{L}$
Platelets count	$\times 10^3/\mu\text{L}$	1	$\times 10^9/\text{L}$
Creatinine	mg/dL	76.25	$\mu\text{mol}/\text{L}$
Total Bilirubin	mg/dL	17.10	$\mu\text{mol}/\text{L}$
Direct Bilirubin	mg/dL	17.10	$\mu\text{mol}/\text{L}$
Indirect Bilirubin	mg/dL	17.10	$\mu\text{mol}/\text{L}$
ALT	U/L	1	U/L
AST	U/L	1	U/L
ALP (Alkaline Phosphatase)	U/L	1	U/L

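### The SAP's creatinine conversion factor is 76.25 where 88.4 is correct, so values converted from mg/dL come out 13.7% too low in the descriptive laboratory output

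*SAP*

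**What the plan says.** SAP 10.9.2 sets the unit for laboratory output: "Presentations will use SI Units". Its instruction for conventional units is "To convert from the conventional unit to the SI unit, multiply by the conversion factor", followed by a table of factors. The creatinine row reads "Creatinine mg/dL 76.25" and gives µmol/L as the SI unit. The three bilirubin rows, also mg/dL to µmol/L, carry 17.10. No other section of the SAP or protocol gives a different creatinine factor.

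The results are used descriptively. The section plans that "Clinical laboratory data will be summarized for each treatment group at each measurement time point", adds changes from baseline and listings with out-of-range flags, and continues "with shift tables summarizing the frequencies of patients below, within, and above the normal ranges at each time point as compared with baseline".

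Serum creatinine is collected at screening, 4 weeks, 3 months and 6 months (Protocol 6.4 and Appendix 3). The results are local: at follow-up visits the investigator is to "check the following local laboratory results". The protocol synopsis states "Approximately 140 study sites in 11 countries are planned to enroll patients in this study", and Protocol section 11 refers to "about 140 study centers in Europe and USA".

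**The concern.** A conversion from mg/dL to µmol/L is fixed by the molar mass of the substance and leaves no room for choice. The creatinine factor in the SAP does not fit creatinine, although the bilirubin factor in the same table does fit bilirubin. A programmer who follows the SAP exactly will therefore produce wrong creatinine values, and nothing else in the documents would alert anyone.

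What is at stake is the accuracy of the reported serum creatinine results: means, medians, ranges, changes from baseline and listings. An error of this size is not obvious on inspection, because a converted value of 76 µmol/L looks as plausible as 88.

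**Working it through.** **Inputs**

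- Factor in the SAP: 76.25, used as SI value = conventional value × factor (SAP 10.9.2).
- Bilirubin factor in the same table: 17.10.
- Atomic masses C 12.011, H 1.008, N 14.007, O 15.999. These and the molecular formulas are physical constants, not taken from the documents.

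**Formula.** 1 mg/dL = 10 mg/L = 10,000 µg/L. Dividing by the molar mass M in g/mol (the same number as µg/µmol) gives the factor in µmol/L per mg/dL: factor = 10,000 / M.

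**Step 1: does the method reproduce a figure in the table?** Bilirubin, C33H36N4O6:
M = 33 × 12.011 + 36 × 1.008 + 4 × 14.007 + 6 × 15.999 = 584.67.
10,000 / 584.67 = 17.10, which matches the SAP. The method and the table's convention agree.

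**Step 2: creatinine**, C4H7N3O:
M = 4 × 12.011 + 7 × 1.008 + 3 × 14.007 + 15.999 = 113.12.
10,000 / 113.12 = 88.40. The SAP's 76.25 is not reproduced.

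**Step 3: where 76.25 may come from.** 10,000 / 76.25 = 131.15 g/mol. Creatine, C4H9N3O2, has M = 131.135 and factor 10,000 / 131.135 = 76.26. The closeness of the match makes a text-extraction fault unlikely. An adjacent line of a conversion list may have been copied, though the documents do not show how it arose.

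**Step 4: size for a converted value.** 76.25 / 88.40 = 0.8625, so the reported value is 13.7% too low.

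| True value (mg/dL) | Reported with 76.25 (µmol/L) | Correct with 88.40 (µmol/L) |
|---|---|---|
| 1.0 | 76.3 | 88.4 |
| 1.5 | 114.4 | 132.6 |
| 2.0 | 152.5 | 176.8 |

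A change from baseline between two converted values is multiplied by the same 0.8625.

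**Step 5: size for a pooled mean.** The share s of values entered in mg/dL is not given and must be assumed. With equal true means in the two unit groups, the relative error is −s × 13.7%.

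| Share converted | Error in pooled mean |
|---|---|
| 0% | 0% |
| 25% | −3.4% |
| 50% | −6.9% |
| 75% | −10.3% |
| 100% | −13.7% |

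**Step 6: shift tables and flags.** The SAP does not say in which unit a value is compared with its normal range.

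- If the comparison is made in the original unit, or the range is multiplied by the same factor, the category does not change.
- If a wrongly converted value is set against a correct range in µmol/L, some high values are classed as normal. With an assumed upper limit of 110 µmol/L, these are values between 110 / 88.40 = 1.24 and 110 / 76.25 = 1.44 mg/dL.

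**Step 7: the red-cell row.** 10^6 per µL × 10^6 µL per L = 10^12 per L, so the factor is 1, where the table has 0.1. Red-cell count is not among the haematology tests in Protocol 6.4 or Appendix 3, so this row changes no result.

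**The case against.** The best case on the other side accepts the arithmetic and disputes the reach. Most of it stands.

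- **Mixed units.** A reader might infer that understated values will be pooled with correct ones from sites that already report µmol/L. Local laboratories in 11 countries make this plausible. However, no section names a site's units or says how the eCRF captures them. If all values arrive in mg/dL, the error is a uniform rescaling. If all arrive in µmol/L, nothing is converted and there is no error.
- **Renal rules.** A reader might also infer that the renal exclusion, the renal discontinuation rule or the renal subgroup is affected. All three are stated in terms of creatinine clearance (Protocol 4.2.2 and 6.5.1; SAP Table 2). Clearance is listed as its own local result in Protocol 6.4 and has no row in the conversion table. Nothing shows that a converted serum value feeds any of them.
- **Shift tables.** The effect depends on programming that the SAP does not describe, so it is possible but not established.
- **Scope.** SAP 10.9.2 plans no test or model for creatinine. The same factor applies to both arms, so no systematic bias towards either is expected, beyond chance differences in the unit mix.

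None of this makes 76.25 a defensible factor. It limits the consequence to descriptive output.

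**Conclusion.** The factor is wrong as written. The correct value is 88.4, and every creatinine value converted under SAP 10.9.2 would be reported 13.7% too low, as would changes between converted values. This rests only on atomic masses and the SAP's own instruction to multiply.

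The effect on pooled summaries lies between 0% and 13.7% low. The documents do not allow a narrower figure, because the share of values in mg/dL is unknown. The effect on shift tables and flags is conditional on how ranges are handled.

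The documents do not support the stronger readings: established mixing of right and wrong values, distortion of the renal eligibility or discontinuation rules or of the renal subgroup, or any effect on the primary endpoint or the comparison between arms. The point is a definite error in a stated rule for reporting a safety laboratory value. It is limited to descriptive tables and listings and should be corrected before they are produced.

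**What to change.** In the SAP 10.9.2 table, replace 76.25 with 88.4 for creatinine. Check the analysis programs for the same factor, and correct and rerun any creatinine output already produced with it. It would help to add one sentence stating whether values are compared with normal ranges in the original unit or after both are converted, since that settles the shift-table question.

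As housekeeping, set the red-cell factor to 1 or delete the row, since the test is not collected.

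The cost is one table cell (two with the red-cell row), an optional sentence and a short program check. Design, data collection, sample size and inferential analyses do not change.

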## STATISTICAL ANALYSIS PLAN

Version: 1.3

Date: 29OCT2019

Sponsor: Fondazione FADOI

Study Protocol: CARAVAGGIO (FADOI 03.2016)

Partial Prothrombin Time (PPT)	Seconds	1	Seconds
--------------------------------	---------	---	---------

### 10.9.3 Vital Signs

Vital signs measurement (systolic BP, diastolic BP, heart rate and, for dalteparin group, body weight) and their changes from baseline will be summarized by visit and treatment group. Individual vital signs measurement will be listed.

### 10.9.4 Interim analyses

Not foreseen.

### 10.9.5 Protocol deviations

An individual data listing of patients who did not satisfy the eligibility criteria will be produced.

A summary table and an individual data listing of major protocol deviations will be prepared.

### 10.9.6 Data and Safety Monitoring Board (DSMB)

An independent DSMB periodically reviews the study outcomes with all information available concerning treatment allocation. A DSMB charter was provided to the board members before the start of the study. The DSMB is composed of three expert clinicians with experience in the conduction and monitoring of clinical trials.

## 11 Programming Conventions for Outputs

### DATES & TIMES

Depending on data available, dates and times will take the form DDMMYY (i.e. 01JAN2019) and hh:mm (i.e. 10:35)

### SPELLING FORMAT

English UK

### PRESENTATION OF TREATMENT GROUPS

For outputs, treatment groups will be represented as follows and in that order:

Treatment Group	For Tables and Listings
Apixaban	Apixaban
LMWH Dalteparin	Dalteparin

### PRESENTATION OF VISITS

For outputs, visits will be represented as follows and in that order:

Long Name (default)	Short Name	Day
Screening	V1	Day -3 or less
Enrolment	V2	Day 1
Week 4	V3	4-week after enrolment
Month 3	V4	3-month after enrolment
End of study Treatment	V5	6-month after enrolment or early withdrawal
End of Study	V6	7-months after randomization

### LISTINGS

All listings will be ordered by the following:

- Treatment group
- Site ID
- Patient ID
- Visit/date/hour (where applicable).

For listings where non-randomized subjects are included, these will appear in a category after the randomized treatment groups labelled “Not Randomized”.

### TEXT CASE

- For titles and column labels, capitalize important words, i.e. nouns, pronouns, verbs, adverbs and adjectives but not articles, conjunctions or prepositions
- All Footnotes will be in sentence case format.
- All symbols used in body of outputs will be footnoted.

## 12 Partial Date Conventions

Imputed dates will NOT be presented in the listings.

### ALGORITHM FOR TREATMENT EMERGENCE OF ADVERSE EVENTS:

START DATE	STOP DATE	ACTION
Known	Known	If start date < study med start date, then not TEAE If start date >= study med start date but ≤ study med end date+30, then TEAE
	Partial	If start date < study med start date, then not TEAE If start date >= study med start date but ≤ study med end date+30, then TEAE
	Missing	If start date < study med start date, then not TEAE If start date >= study med start date but ≤ study med end date+30, then TEAE
Partial, but known components show that it cannot be on or after study med start date	Known	Not TEAE
	Partial	Not TEAE
	Missing	Not TEAE
Partial, could be on or after study med start date	Known	If stop date < study med start date, then not TEAE If stop date >= study med start date but ≤ study med end date+30, then TEAE
	Partial	Impute stop date as latest possible date (i.e. last day of month if day unknown or 31st December if day and month are unknown), then: If stop date < study med start date, then not TEAE If stop date >= study med start date but ≤ study med end date+30, then TEAE
	Missing	Assumed TEAE
Missing	Known	If stop date < study med start date, then not TEAE If stop date >= study med start date but ≤ study med end date+30, then TEAE
	Partial	Impute stop date as latest possible date (i.e. last day of month if day unknown or 31st December if day and month are unknown), then: If stop date < study med start date, then not TEAE If stop date >= study med start date but ≤ study med end date+30, then TEAE
	Missing	Assumed TEAE

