Adverse events can be spontaneously reported or elicited during open-ended questioning, examination, or evaluation of a subject. In order to prevent reporting bias, subjects should not be questioned regarding the specific occurrence of one or more AEs. If known, the diagnosis of the underlying illness or disorder should be recorded, rather than its individual symptoms. The following information should be captured for all AEs: onset, duration, intensity, seriousness, relationship to investigational product, action taken and treatment required and outcome. If treatment for the AE was administered, it should be recorded on the appropriate eCRF page.

The Investigator's assessment must be clearly documented in the site's source documentation with the Investigator's signature.

Investigator should follow subjects with AEs until the event has resolved or the condition has stabilized.

In case of unresolved AEs including significant abnormal laboratory values at the end of study assessment, these events will be followed up until resolution or until they become clinically not relevant.

The investigator shall supply the Promoter and Ethics Committee with any additional requested information, notably for reported deaths of subjects. Possible additional information on the AE collected/identified during the study will be reported on the eCRF.

9.2.1 Serious Adverse Event Collection and Reporting for Investigators

Following the subject's or the legal representative's written consent to participate in the study, all AEs, SAEs, AESIs, bleeding outcomes and study outcomes will be captured in the eCRF.

Study outcomes are clinically anticipated events and will be periodically reviewed by the DSMB to ensure prompt identification of any clinically concerning safety issues. Study outcomes (suspected recurrent DVT or PE, major bleedings, clinically relevant non-major bleedings, MI, stroke, and venous thrombotic events at other locations) will be exempted from expedited safety reports of suspected unexpected serious adverse reactions

(SUSARs) to regulatory authorities, Investigators, IECs, and IRBs. All SAEs resulting in death, regardless of whether they are waived endpoint events, will be captured in the Promoter's global safety database.

The following types of events whether related or not related to study drug, must be reported within 24 hours of the Investigator's awareness, to the Contract Research Organization Exom Group:

- SAEs
- AESIs

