### 10.9.1 Adverse events

All adverse events recorded during the treatment period and up to 30 days after the last study dose intake will be summarized by treatment group with descriptive statistics for the Safety population.

All adverse events will be assigned to a Preferred Term (PT) and will be classified by primary System Organ Class (SOC) according to the MedDRA thesaurus version 20.1. Adverse events will be reported on a per-patient basis. This means that even if a patient reports the same event repeatedly (i.e. events mapped to the preferred term) the event will be counted only once. In the latter case, the event will be assigned the worst intensity and the strongest relationship to the study drug.

For summaries, the drug-event relationship will be shown as “*Related*” if relationship with study treatment is assessed as “*Certain*”, “*Probable*” or “*Possible*” by the Investigator; otherwise the event is considered as “*Unrelated*”. Missing categories will be considered as related.

Treatment emergent events, defined as those AEs that start or worsen after the start of apixaban/dalteparin and up to 30 days after the last study dose intake, will be summarized by treatment group, System Organ Class, and Preferred Term, and also by event severity and by the event’s relationship to study treatment.

The following listing and tables will be presented:

- 1) An overview of adverse events with the number of patients who exhibited at least one AE, number of adverse events, number of patients who exhibited at least one TEAE, number of TEAEs, number of patients who reported at least one related TEAE, number of related TEAEs, number of patients who reported at least one treatment-emergent serious adverse event (TESAE), number of TESAEs, number of patients who reported at least one related TESAE, number of related TESAEs, number of patients who reported at least one AESI, number of AESI, number of patients who died, number of patients who temporarily discontinued the study drug due to an adverse event, number of patients with premature

withdrawal due to an adverse event;

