- 15) List of AESI by patient;
- 16) List of Patients with Adverse Events Leading to Withdrawal from study drug;
- 17) List of Patients with Adverse Events Leading to temporary discontinuation of study drug.

The number and the percentage of patients with at least one TEAEs by SOC and Preferred Term, and the number of events will be presented for the statistical summary from the above points #3 to

#9.

Adverse events with start date before the first study dose intake or after 30 days the last study dose intake will be only listed.

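### For adverse events with an incomplete start date, SAP section 12 tests the stop date and not the onset against last dose + 30 days, so late-stopping events get no class and are not counted as treatment-emergent

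*SAP*

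**What the plan says.** SAP 10.9.1 defines treatment-emergent events as "those AEs that start or worsen after the start of apixaban/dalteparin and up to 30 days after the last study dose intake". The same section decides by start date which events stay out of the summaries: "Adverse events with start date before the first study dose intake or after 30 days the last study dose intake will be only listed".

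The table for treatment emergence in SAP section 12 follows that definition when the start date is known: "If start date >= study med start date but ≤ study med end date+30, then TEAE". The stop date plays no part in those rows.

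When the start date is missing, or is partial but could fall on or after first dose, the table turns to the stop date. If the stop date is before first dose, the event is not a TEAE. Otherwise the condition is "If stop date >= study med start date but ≤ study med end date+30, then TEAE". A partial stop date is handled first by the instruction "Impute stop date as latest possible date", meaning month end or 31 December, and is then put to the same test. If the stop date is missing altogether, the event is assumed to be a TEAE. No cell says what to do when the stop date is later than last dose + 30 days.

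**The concern.** When an event resolved does not show when it began. Four cells (start partial or missing, crossed with stop known or partial) use the stop date for both ends of the window. At the lower end this is sound, because an event that ended before first dose cannot have started on treatment. At the upper end it is not: an event can begin on treatment and resolve well after last dose + 30 days.

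The latest-date imputation adds to this. It is cautious at the lower end, but at the upper end it moves events past the limit and out of the count.

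At stake is the completeness of the TEAE and serious TEAE tables and lists in SAP 10.9.1, including the overview of TEAEs that are study outcomes. A programmer who codes the four cells literally will leave these events out.

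**Working it through.** The documents state no figure for this rule, so there is none to reproduce. The check is to run the section 12 table on test events and compare the results with 10.9.1.

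Inputs from the SAP: the known-start rule, the stop-date rule, the latest-date imputation and the missing-stop rule, all in the section 12 table, and the onset-based definition in 10.9.1. Assumed for illustration: first dose 10 January 2018 and 180 days of treatment. Last dose is then 10 January + 179 days = 8 July 2018, and the limit is 8 July + 30 days = 7 August 2018.

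| Event | Start recorded | Stop recorded | Date tested against 7 Aug 2018 | Result as written |
|---|---|---|---|---|
| 1 | 15 Mar 2018 | 20 Aug 2018 | start, 15 Mar | TEAE |
| 2 | Mar 2018 | 20 Aug 2018 | stop, 20 Aug | no rule applies |
| 3 | Mar 2018 | 1 Aug 2018 | stop, 1 Aug | TEAE |
| 4 | Mar 2018 | missing | none | TEAE (assumed) |
| 5 | Mar 2018 | Aug 2018 | stop, imputed to 31 Aug | no rule applies |
| 6 | Mar 2018 | 2018 | stop, imputed to 31 Dec | no rule applies |
| 7 | missing | 20 Aug 2018 | stop, 20 Aug | no rule applies |

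Reading across:

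- Events 1 and 2 differ only in that the day of onset is missing. March 2018 lies wholly within treatment, so both satisfy 10.9.1, but only event 1 is flagged.
- Events 2 and 4 differ only in that a recovery date was recorded. Recording it takes the event out of the count.
- Event 5 may have stopped on or before 7 August. The imputation alone puts it over the limit.
- Event 7 could have begun before, during or after the window. The table assumes a TEAE when the stop is also missing, but gives no answer when the stop is known and late.

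The companion table in section 12, for prior and concomitant medications, handles the same problem differently. There the stop date serves only to identify prior medications. The start date, imputed to its earliest value if partial, is compared with end of treatment. A medication with a missing start and a stop on or after first dose is concomitant, with no upper limit on the stop.

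Late stop dates can be expected. Protocol 9.2 says "Investigator should follow subjects with AEs until the event has resolved or the condition has stabilized", and Protocol 6.6 follows all randomized patients for 7 months, including those who stopped drug early. For a patient who stops at 3 months (the mean discontinuation time assumed in Protocol 10.1), the limit falls at about month 4, with about 7 − 4 = 3 months of scheduled follow-up remaining.

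Under the proposed rule, events 2, 5 and 6 have an earliest possible start of 1 March 2018, which is before 7 August, so they become TEAEs like event 1. Event 7 did not end before first dose and has no start component to test, so it is assumed to be a TEAE. Events 3 and 4 do not change. An event recorded as starting in September 2018 has an earliest start of 1 September, after 7 August, and is not a TEAE, as 10.9.1 requires.

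**The case against.** The best defence is that this is a gap and not a stated exclusion. No cell labels a late-stopping event as not treatment-emergent, and the definition in 10.9.1 still governs, so a careful programmer could fill the gap correctly. The first part is right. But the cells still apply the wrong test, and the result should not depend on who writes the code.

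The reach is also narrow. Only events with an incomplete start and a recorded stop after the limit are touched. Collection is targeted (Protocol 9.2), onset is to be captured for every event, and serious events are reported within 24 hours of awareness. For patients who complete six months, the limit falls at about the 7-month visit. All of this stands.

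Three stronger readings are tempting, and the documents do not support them.

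- A reader might infer that the rule removes the longest-lasting events. It does not: events with no stop date, which include those never resolved, are kept. What matters is where the stop date falls in the calendar, and a short event near the end of the window can be caught too.
- A reader might infer that every affected event began on treatment. A start recorded only as the month of first dose could precede that dose, and a missing start says nothing about onset.
- A reader might infer that harm is hidden or that one arm is favoured. The rule is the same in both arms. The overview also counts all adverse events separately from TEAEs, and the listings of deaths and of events leading to withdrawal or interruption are not titled as restricted to TEAEs.

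**Conclusion.** The point holds as a minor fault in a stated rule. In four cells of the section 12 table the 30-day limit is put on the stop date, although 10.9.1 and the known-start rows put it on onset. An event with a possible on-treatment onset that stops after last dose + 30 days is left without a class and, if the table is followed as written, is missing from the TEAE and serious TEAE outputs.

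The number of such events cannot be derived from the documents and is probably small. That judgement rests on onset dates being recorded well, as Protocol 9.2 intends. The primary efficacy analysis does not use the rule, and the bleeding analysis has its own on-treatment window of 72 hours after last dose. The dates in the worked example are assumptions. They show how the rule behaves, not how often it matters.

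**What to change.** In the four cells (start missing, or partial and possibly on or after first dose; stop known or partial), replace the present condition with three steps:

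1. If the stop date, imputed to its latest value when partial, is before first dose, the event is not a TEAE.
2. If the start is partial and its earliest possible date is after last dose + 30 days, the event is not a TEAE.
3. Otherwise, assume TEAE.

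Step 2 is needed. Merely deleting the upper limit on the stop date would let in events whose recorded month of onset lies wholly after the window, contrary to 10.9.1.

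The cost is four table cells and the matching code. A few events with a missing start and a true onset outside the window may be counted as TEAEs, which is the conservative direction for safety. The primary efficacy analysis and the 72-hour bleeding window are not affected.
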